11.1 ADVERSE EVENTS

Adverse events will be coded by system organ class and preferred term using the *MedDRA*, version 22.0 or newer.

An AE will be considered a treatment-emergent adverse event (TEAE) if the AE began or worsened (increased in severity or became serious) on or after the date of the first dose of investigational product. However, an AE that occurs more than 30 days after the last dose of study intervention will not be counted as a TEAE. Per eCRF instructions, a new AE record will be created with a new AE onset date for any AE that worsens. Therefore, TEAEs can simply be identified as those AEs with recorded onset date on or after the date of the first dose of investigational product and within 30 days after the last dose of investigational product. If more than 1 AE was reported before the date of the first dose of investigational product and coded to the same preferred term, the AE with the greatest severity will be used as the benchmark for comparison with the AEs occurring during the double-blind treatment period or during the double-blind down-taper period that were also coded to that preferred term.

The number and percentage of patients reporting TEAEs in each treatment group will be tabulated by system organ class and preferred term and further categorized by severity and causal relationship to the investigational product, for both the double-blind treatment period and the double-blind down-taper period, separately. If more than 1 AE is coded to the same preferred term for the same patient, the patient will be counted only once for that preferred term using the greatest severity and strictest causality for the summarization by severity and by causal relationship to the investigational product, respectively.

The distribution of TEAEs by severity and causal relationship to the investigational product will be summarized by treatment group separately for the double-blind treatment period and the double-blind down-taper period. Common TEAE during the double-blind treatment period is defined in 2 ways: $\geq 1\%$ of patients in any treatment group and $\geq 2\%$ of patients in any treatment group. The incidence of common TEAEs will be summarized separately by preferred term, and treatment group and will be sorted by decreasing frequency for the levomilnacipran treatment group.

An AE will be considered a treatment-emergent serious adverse event (TESAE) if it is a TEAE that additionally meets any serious adverse event (SAE) criterion.

The number and percentage of patients who have TESAEs will be summarized by preferred term and treatment group and will be sorted by decreasing frequency for the levomilnacipran treatment groups.

The number and percentage of patients in the Safety Population who have AEs leading to premature discontinuation of the investigational product will be summarized by preferred term and treatment group and will be sorted by decreasing frequency for the levomilnacipran treatment group.

Listings will be presented for patients with SAEs, patients with AEs leading to discontinuation, and patients who died (if any) for the Screened Population. All patients with SAEs, including those reported during the screening period or more than 30 days after the date of the last dose of the double-blind investigational product, and patients discontinuing because of AEs before taking double-blind investigational product will be included in these listings.

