9.7.6.1 Adverse Events

An AE (classified by preferred term) that occurs during the double-blind treatment period or during the double-blind down-taper treatment period will be considered a treatment-emergent adverse event (TEAE) if it was not present before the date of the first dose of double-blind investigational product or was present before the date of the first dose of double-blind investigational product and increased in severity during the double-blind treatment period or during the double-blind down-taper period, respectively. If more than 1 AE is reported before the date of the first dose of double-blind investigational product and coded to the same preferred term, the AE with the greatest severity will be used as the benchmark for comparison with the AEs occurring during the double-blind treatment period or during the double-blind down-taper period that were also coded to that preferred term. An AE that occurs more than 30 days after the date of the last dose of double-blind investigational product will not be counted as a TEAE.

An AE occurring during the double-blind down-taper period will be considered a newly emergent AE if it was not present before the start of the double-blind down-taper period or was present before the start of the double-blind down-taper period but increased in severity during the double-blind down-taper period. The newly emergent AEs during the double-blind down-taper period will be summarized by body system, preferred term, and treatment group.

The number and percentage of patients reporting TEAEs in each treatment group will be tabulated by system organ class and preferred term; by system organ class, preferred term, and severity; and by system organ class, preferred term, and causal relationship to the investigational product. If more than 1 AE is coded to the same preferred term for the same patient, the patient will be counted only once for that preferred term using the most severe and most related occurrence for the summarization by severity and by causal relationship to the investigational product.

The distribution of TEAEs by severity and causal relationship to the investigational product will be summarized by treatment group.

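### SAP 11.1 flags treatment-emergent AEs by onset date alone and omits the newly emergent AE analysis for the taper, two undeclared departures from Protocol 9.7.6.1

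*SAP*

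**What the plan says.** **SAP 11.1.** An AE is a TEAE "if the AE began or worsened (increased in severity or became serious) on or after the date of the first dose". The SAP then relies on an eCRF instruction that "a new AE record will be created with a new AE onset date for any AE that worsens". From this it concludes that "TEAEs can simply be identified as those AEs with recorded onset date on or after the date of the first dose of investigational product", subject to a 30-day limit after the last dose. The next sentence deals with a preferred term that a patient reported more than once before dosing. For that case, "the AE with the greatest severity will be used as the benchmark for comparison with the AEs occurring during the double-blind treatment period"; taper events are covered in the same way. The sentence does not say what follows from the comparison. TEAEs are then tabulated separately for the treatment period and the down-taper.

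**Protocol 9.7.6.1.** AEs are classified by preferred term. A term is treatment-emergent if it was absent before first dose, or if it "was present before the date of the first dose of double-blind investigational product and increased in severity during the double-blind treatment period", with a parallel clause for the taper. The protocol adds a second concept with a later reference point: "An AE occurring during the double-blind down-taper period will be considered a newly emergent AE if it was not present before the start" (meaning the taper's start), or if it was present earlier and then worsened during the taper. It commits to an output: "The newly emergent AEs during the double-blind down-taper period will be summarized by body system, preferred term, and treatment group".

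**SAP 18.0.** No changes from the protocol's analyses are declared.

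**The concern.** The eCRF instruction explains why the onset date captures worsening: a worsened event gets a new record. It does nothing to screen out a resolved pre-dose event that comes back at equal or lower severity, because that recurrence also gets a new record with a post-dose onset. The protocol excludes such events. The SAP includes them, and still carries a benchmark sentence that an onset-date flag never applies. A programmer has to guess whether that sentence matters.

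Pre-dose AEs are to be expected in this trial. They are recorded from consent, and screening with washout usually lasts one week but may run to five (Protocol 9.1, 9.5.2.1, 9.5.5). The TEAE flag feeds the tables by system organ class and preferred term, severity and causality, the common-TEAE lists, the treatment-emergent SAE table and the interim safety tables (SAP 11.1, SAP Appendix III).

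For the down-taper, the protocol's newly emergent table separates events that start or worsen in that week from repeats of events already seen on treatment. Without it, the only taper AE summary in SAP 11.1 is referenced to the first dose and cannot make that separation.

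**Working it through.** The plan gives no figure to reproduce here, so the check applies each rule to the same example histories. The protocol columns follow Protocol 9.7.6.1, where severity must exceed the worst earlier severity of that preferred term. For newly emergent events the protocol does not say which earlier severity is the comparator; the worst is assumed below.

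*Events with onset in the treatment period*

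| History of one preferred term | SAP onset-date rule | Protocol TEAE rule |
|---|---|---|
| No pre-dose event; mild on treatment | TEAE | TEAE |
| Pre-dose mild and moderate, resolved; new mild or moderate episode | TEAE | not a TEAE |
| Pre-dose mild and moderate; severe episode | TEAE | TEAE |
| One pre-dose mild event, resolved; new mild episode | TEAE | not a TEAE |

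In the second row the SAP's benchmark sentence applies but states no result. In the fourth row it is silent, because only one pre-dose AE exists. In the protocol the same sentence is harmless: the main rule already handles a single pre-dose AE, and the benchmark only settles which severity to use when there are several. The SAP replaced the main rule and left the sentence with nothing to act on.

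A related difference: a pre-dose event that becomes serious at unchanged severity has worsened under the SAP but not under the protocol, which names only severity.

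*Events with onset in the down-taper*

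| History of one preferred term | SAP taper TEAE | Protocol taper TEAE | Protocol newly emergent |
|---|---|---|---|
| No earlier event; first onset in taper | yes | yes | yes |
| Mild on treatment; moderate in taper | yes | yes | yes |
| Mild on treatment, resolved; mild in taper | yes | yes | no |
| Pre-dose mild and moderate; mild in taper | yes | no | no |

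The third row shows what the missing table would screen out. An event that simply continues into the taper gets no new record and is not affected.

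*Scale.* Inputs: 160 planned per arm (SAP 4.0), all assumed treated; common-TEAE cut-offs of at least 1% and at least 2% in any arm (SAP 11.1).

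- One patient: 1/160 = 0.625%.
- 1% cut-off: 0.01 × 160 = 1.6, so 2 patients (2/160 = 1.25%; 1 patient gives 0.625%).
- 2% cut-off: 0.02 × 160 = 3.2, so 4 patients (4/160 = 2.5%; 3 patients give 1.875%).

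The documents give no recurrence rates. If between 1 and 8 patients per arm were reclassified for a term (an assumption), its incidence would move by 1/160 = 0.6 to 8/160 = 5.0 percentage points.

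**The case against.** The strongest reply has four parts.

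- **The SAP is nearly consistent with itself.** Its opening definition and the onset-date shortcut agree, given the eCRF instruction. The benchmark sentence covers only multiple pre-dose AEs and leads nowhere, so it may be leftover protocol text. This stands in part. A reader might infer that SAP 11.1 holds two complete TEAE rules that clash at every recurrence; it does not. But if the sentence is a leftover, the SAP has left the protocol's rule without saying so. Nor is it plainly inert: SAP 16.6 imputes missing pre-dose severity as mild for use in the incidence summary, which has an obvious role in a severity comparison and little role under an onset-date rule.
- **The protocol's own taper TEAEs also use first dose as the reference.** This stands. A reader might infer that the SAP alone turns repeats of on-treatment events into taper TEAEs; under both documents they can be counted. What the SAP lacks is the separate newly emergent analysis.
- **Table specifications are in a separate document (SAP 4.0).** The table may exist there, and that cannot be checked. But a table shell does not supply a definition that the SAP omits.
- **Safety is descriptive.** This stands. No test, power or type I error depends on the flag, and the listings of SAEs and of AEs leading to discontinuation do not rest on it.

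**Conclusion.** The point holds in a limited form. SAP 11.1 counts same-or-lower-severity recurrences of pre-dose AEs that Protocol 9.7.6.1 excludes, keeps a benchmark sentence that its own rule does not use, and omits the protocol's newly emergent AE definition and table. SAP 18.0 declares none of this.

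The consequence is confined to reported AE incidence. Its size cannot be derived from the documents. What can be said is that one reclassified patient is 0.625 points in an arm of 160 and can decide whether a term appears on a common-TEAE list. A reader might go further and infer a definite distortion of relative risks between arms, or a spurious withdrawal signal in the taper. Neither is supported: no recurrence rates are given, no relative-risk analysis of AEs is planned, and a taper TEAE table and a newly emergent table answer different questions, so their counts are not rival estimates of one quantity.

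**What to change.** State one TEAE rule in SAP 11.1, by either route.

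- **(a) Apply the protocol.** Count an AE with onset from first dose to 30 days after last dose if there was no pre-dose AE with that preferred term, or if its severity exceeds the worst pre-dose severity of that term. Extend the benchmark to one or more pre-dose AEs and delete the onset-date shortcut sentence. If becoming serious is kept as a form of worsening, declare it in SAP 18.0, because it is not in the protocol's rule.
- **(b) Keep the onset-date rule.** Delete the benchmark sentence and declare the departure in SAP 18.0.

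In either case, restore the Protocol 9.7.6.1 definition and table of newly emergent AEs for the down-taper, using the start of that period as defined in SAP 11.0. State which earlier severity is the comparator when a term was recorded more than once before the taper.

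The cost is SAP wording, one flag in the AE dataset and one table. No new data are needed.

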11.2 CLINICAL LABORATORY PARAMETERS

Descriptive statistics for clinical laboratory values (in SI units) and changes from the baseline values at each assessment time point (including the end of the double-blind treatment period) will be presented by treatment group for the following laboratory parameters:

Hematology: Absolute and differential white blood cell count, erythrocyte count, hemoglobin, hematocrit, platelet count, and red blood cell indices (mean corpuscular volume, mean corpuscular hemoglobin, and mean corpuscular hemoglobin concentration)

Chemistry: Sodium, potassium, calcium, chloride, bicarbonate, glucose, blood urea nitrogen, creatinine, total protein, alkaline phosphatase, albumin, total bilirubin, direct bilirubin, indirect bilirubin, AST, ALT, Free T3, free T4, TSH, lactate dehydrogenase, creatine phosphokinase, γ -glutamyl transpeptidase, uric acid, phosphate, lipid panel (total cholesterol, triglycerides, low density lipoproteins, high density lipoproteins), prolactin, insulin, and magnesium

Urinalysis: Specific gravity, pH, protein, glucose

In addition, descriptive statistics for values and changes from the baseline values in conventional units at each assessment time point will be presented for selected clinical laboratory parameters listed in Appendix II.

Clinical laboratory test values will be considered potentially clinically significant (PCS) if they meet either the lower-limit or higher-limit PCS criteria listed in Table 11–1. The number and percentage of patients who have PCS postbaseline clinical laboratory values will be tabulated by treatment group. The percentages will be calculated relative to the number of patients with available non-PCS baseline values and at least 1 postbaseline assessment. The numerator will be the total number of patients with available non-PCS baseline values and at least 1 PCS postbaseline value. A supportive listing of patients with PCS postbaseline values will be provided, including the patient identification (PID) number, and baseline and all postbaseline (including non-PCS) values. In addition, a listing of all AEs that occurred in patients who had PCS postbaseline clinical laboratory values will be provided.

Table 11–1 Criteria for Potentially Clinically Significant Laboratory Values

Parameter	SI Unit	Lower Limit	Higher Limit
HEMATOLOGY			
Basophils	%		> 6
Eosinophils	%		> 10
Hematocrit	ratio	< 0.9 × LLN	_
Hemoglobin	g/L	< 0.9 × LLN	_
Lymphocytes	%	< 10	> 60
Monocytes	%	_	> 20
Neutrophils	%	< 30	> 90
Platelet count	$\times 10^9/L$	≤ 75	≥ 700
White blood cell count	$\times 10^9/L$	≤ 2.5	≥ 15
CHEMISTRY			
Albumin	g/L	< 0.9 × LLN	> 1.1 × ULN
Alkaline phosphatase	U/L	_	\geq 3 × ULN
Alanine aminotransferase	U/L	_	\geq 3 × ULN
Aspartate aminotransferase	U/L	_	\geq 3 × ULN
Bicarbonate	mmol/L	< 0.9 × LLN	> 1.1 × ULN
Blood urea nitrogen	mmol/L	_	> 1.2 × ULN
Calcium	mmol/L	< 0.9 × LLN	> 1.1 × ULN
Chloride	mmol/L	< 0.9 × LLN	> 1.1 × ULN
Cholesterol, total	mmol/L	_	> 1.3 × ULN
Creatinine	μmol/L	_	> 1.3 × ULN
Glucose	mmol/L	< 0.8 × LLN	> 1.4 × ULN
High-density lipoprotein	mmol/L	< 0.8 × LLN	_
Low-density lipoprotein	mmol/L	_	> 2.0 × ULN
Magnesium	mmol/L	< 0.9 × LLN	> 1.1 × ULN
Phosphate	mmol/L	< 0.9 × LLN	> 1.1 × ULN
Potassium	mmol/L	< 1.0 × LLN	> 1.0 × ULN
Sodium	mmol/L	< 1.0 × LLN	> 1.0 × ULN
Total bilirubin	μmol/L	_	> 1.5 × ULN
Total protein	g/L	< 0.9 × LLN	> 1.1 × ULN
Triglyceride	mmol/L	_	> 3.0 × ULN
URINALYSIS			•
Protein	mg/dL	_	at least 2 +
Glucose	mmol/L	_	at least 2 +
		·	•

ALT = alanine aminotransferase; AST = aspartate aminotransferase; CPK = creatine phosphokinase; LLN = lower limit of normal value provided by the laboratory; PCS = potentially clinically significant; SI = Le Système International d'Unités (International System of Units); ULN = upper limit of normal value provided by the laboratory.

Shift tables from baseline to end of double-blind treatment period for clinical laboratory parameters will be presented by treatment group for the following categories: low, normal, and high.

Potential Hy's Law criteria is defined by a postbaseline elevation of alanine aminotransferase (ALT) or aspartate aminotransferase (AST) \geq 3x ULN (ULN = upper limit of normal laboratory reference range), along with total bilirubin (TBL) \geq 2x ULN and a non-elevated alkaline phosphatase (ALP) < 2x ULN, all based on blood draws collected within a 24-hour period. The number and percentage of patients who meet the following criteria of clinical interest during the double-blind treatment period will be tabulated by treatment group. A supportive list will also be provided.

- ALT: $\geq 3x$ ULN, $\geq 5x$ ULN, $\geq 10x$ ULN, $\geq 20x$ ULN
- AST: $\geq 3x$ ULN, $\geq 5x$ ULN, $\geq 10x$ ULN, $\geq 20x$ ULN
- ALT or AST: $\geq 3x$ ULN, $\geq 5x$ ULN, $\geq 10x$ ULN, $\geq 20x$ ULN
- TBL: $\geq 2x$ ULN
- ALP: $\geq 1.5 x ULN$
- Concurrent elevations: ALT or AST ≥ 3x ULN with TBL ≥ 1.5x ULN; ALT or AST ≥ 3x ULN with TBL ≥ 2x ULN; ALT or AST ≥ 3x ULN with TBL ≥ 2x ULN and ALP < 2x ULN.

11.3 VITAL SIGNS

Descriptive statistics for vital signs (sitting radial pulse rate, sitting systolic and diastolic blood pressure, body weight and height) and changes from baseline values at each visit, and at the end of double-blind treatment period, and at the end of double-blind downtaper period will be presented by treatment group. Only patients with available baseline and at least 1 postbaseline assessment will be included in the summary. Vital sign values will be considered PCS if they meet both the observed-value criteria and the change-from-baseline criteria listed in Table 11–2. The number and percentage of patients with PCS postbaseline values will be tabulated by treatment group separately for the double-blind treatment period and the double-blind down-taper period. The percentages will be calculated relative to the number of patients with available baseline and at least 1 postbaseline assessment. The numerator will be the total number of patients with available baseline values and at least 1 PCS postbaseline value. A supportive listing of patients with PCS postbaseline values will be provided, including the PID number, and baseline and all postbaseline (including non-PCS) values.

In addition, a listing of all AEs that occurred in patients who had PCS postbaseline vital sign values will be provided.

	Table 11–2.	Criteria for	Potentially	Clinically	Significant	Vital Signs
--	--------------------	--------------	-------------	------------	-------------	-------------

		Criteria ^a			
Parameter	Flag	Observed Value	Change From Baseline		
Sitting systolic blood	High	≥ 140	Increase of ≥ 20		
pressure, mm Hg	Low	≤ 80	Decrease of ≥ 20		
Sitting diastolic blood	High	≥ 100	Increase of ≥ 15		
pressure, mm Hg	Low	≤ 50	Decrease of ≥ 15		
0:44:	High	≥ 130	Increase of ≥ 15		
Sitting pulse rate, bpm	Low	≤ 45	Decrease of ≥ 15		
Waisht Isa	High	_	Increase of ≥ 7%		
Weight, kg	Low	_	Decrease of ≥ 7%		

a A postbaseline value is considered potentially clinically significant if it meets both the observed-value and the change-from-baseline criteria.

bpm = beats per minute.

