9.4.4 Selection of Dosages in the Study

Doses of levomilnacipran in pediatric patients (7-17 years of age) were selected based on modeling of available PK data submitted with NDA 204,168 from the adult healthy volunteers and patients with MDD, as well as adolescent patients (12-17 years of age, LVM-MD-11, 2017) with MDD. Based on the results of modeling a common dosing scheme for both age groups of 7-11 and 12-17 years is appropriate. While the adolescent age group, 12-17 years of age, demonstrates similar plasma concentrations as adults administered the same dose of 80 mg/day, for the younger age group, 7-11 years of age, data indicate that equivalent concentrations are achieved with approximately a 33% dose reduction. Thus, 80 mg/day is expected to show exposure similar to exposures seen for the adult population administered 120 mg/day.

Based on the above findings, levomilnacipran 40 mg/day, with an optional increase to 80 mg/day based on therapeutic response and tolerability, is appropriate for the pediatric patient age range (7-17 years of age). The corresponding plasma concentrations of these doses in pediatric patients are expected to remain within the plasma concentrations associated with the approved therapeutic dose range for adults.

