Vital sign values will be PCS if they meet both the observed-value criteria and the change from baseline-value criteria. The criteria for PCS vital sign values will be detailed in the Statistical Analysis Plan. The percentages will be calculated relative to the number of patients with baseline values and at least 1 postbaseline assessment. The numerator will be the total number of patients with available baseline values and at least 1 PCS postbaseline value. A supportive listing of patients with PCS postbaseline values will be provided, including the PID number, study center number, and baseline and postbaseline values.

9.7.6.4 *Electrocardiogram*

Descriptive statistics for ECG parameters (ie, ventricular heart rate, RR interval, PR interval, QRS interval, QT interval, and QTc interval) and changes from baseline values at each assessment time point will be presented by treatment group. The QTc interval is calculated using the Bazett and Frederica corrections.

The number and percentage of patients with PCS postbaseline ECG values will be tabulated by treatment group. The criteria for PCS ECG values will be detailed in the Statistical Analysis Plan. The percentages will be calculated relative to the number of patients with available non-PCS baseline values and at least 1 postbaseline assessment. The numerator will be the total number of patients with available non-PCS baseline values and at least 1 PCS postbaseline value. A supportive listing of patients with PCS postbaseline values will be provided, including the PID number, study center number, and baseline and postbaseline values.

A listing of patients with postbaseline clinically significant ECG abnormalities, as reported by the Investigator or by the central cardiologist, will also be provided.

The number and percentage of patients with an increase > 30 msec but ≤ 60 msec, and with an increase > 60 msec in QTcF will be tabulated. A supportive listing of patients with postbaseline QTcF increases > 30 msec will be provided, including the PID number, study center, and all QTcF values (including changes from baseline). A listing of all AEs for patients with postbaseline QTcF increases > 30 msec will also be provided.

9.7.6.5 *Other Safety Parameters*

9.7.6.5.1 *Columbia-Suicide Severity Rating Scale*

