11.5.2 Growth Evaluation

Weight and height will be presented as standardized z-scores adjusted for gender and age, using the LMS method (Cole T.J., 1990).

To assess the impact of treatment on growth, the change from baseline to Week 8 in the age-and-gender-adjusted height and weight will be analyzed using an ANOVA model with treatment as factor. A non-parametric (Wilcoxon) test will also be performed.

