12.0 HEALTH OUTCOMES ANALYSES

Not applicable.

13.0 INTERIM ANALYSIS

The interim analysis will be conducted when at least 50% of randomized patients have either completed or discontinued the study. A futility analysis and safety analysis will be included in the interim analysis listed in the Appendix III. The general data derivation and preparation will follow the specification in the SAP and the amendment.

The futility assessment of the primary efficacy parameter (CDRS-R total score) on ITT population will be based on the conditional power as described in Lan et al. (1988) and Proschan et al. (2006). In calculating the conditional power, it is assumed that the future patients to be enrolled into the Study will have similar efficacy as those of the existing patients of the same treatment group. The non-binding futility criteria will be met when the conditional power for detecting a statistically significant treatment difference between the levomilnacipran treatment group (40-80 mg/day) and placebo at the final analysis given the interim analysis results is 0.2 (20%) or lower. Further details of the calculation of conditional power are provided in Appendix IV.

The safety analysis will be performed on the Safety Population, including the summary of TEAE, SAE, death, and TEAE leading to study discontinuation; the incidence of common TEAEs (≥ 2%); PCS for laboratory parameters, vital signs, and ECGs; and the summary of C-SSRS during the double-blind treatment period.

Data will be presented in an unblinded fashion. A separate, independent, fire-walled Statistical Analysis Group and Data Review Committee will be established to conduct the unblinded interim analysis, review the unblinded results and make recommendations regarding the continuation of the study. To maintain the scientific reliability of statistical analyses after the final database lock, preserve the integrity of study conduct, and guard from introducing any potential bias into the conduct of the study and/or analysis of its results, individuals in these two groups will not be involved in any operational aspects of the trial.

14.0 DETERMINATION OF SAMPLE SIZE

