APPENDIX III. STATISTICAL ANALYSIS LIST FOR FUTILITY ANALYSIS

Table 20–2 List of Statistical Analysis for Futility Analysis

Table ID	Title	Analysis Population	
14.1-1.1	Disposition of Participants	Screened Population	
14.1-4.1.1A	Demographics	Safety Population	
14.1-4.1.3	Baseline Characteristics and Efficacy Variables	Intent-to-Treat Population	
14.2-1.1	CDRS-R Total Score: Summary of Baseline, Post-	Intent-to-Treat Population	
	baseline and Analysis of Change from Baseline - MMRM		
14.2-2.1	CGI-S Score: Summary of Baseline, Post-baseline	Intent-to-Treat Population	
11.2 2.1	and Analysis of Change from Baseline - MMRM	intent to Treat repairment	
14.3-1.1	Extent of Exposure	Safety Population	
14.3-2.1.A	Adverse Events: Overall Number (%) of	Safety Population	
	Participants with Adverse Events During the		
	Double-Blind Treatment Period		
14.3-2.2.A	Treatment-Emergent Adverse Events: Number (%)	Safety Population	
	of Participants with Treatment-Emergent Adverse		
	Events During the Double-Blind Treatment Period		
	by Treatment Group, System Organ Class and		
	Preferred Term		
14.3-2.3.A	Common (≥ 2%) Treatment-Emergent Adverse	Safety Population	
	Events: Number (%) of Participants by Preferred		
	Term During the Double-blind Treatment Period		
14.3-4.1	Laboratory Parameters: Number (%) of	Safety Population	
	Participants with Post-baseline Potentially		
	Clinically Significant Values During the Double-		
14251	blind Treatment Period	C.C. D. L.C.	
14.3-5.1	Vital Sign Parameters: Number (%) of Participants	Safety Population	
	with Post-baseline Potentially Clinically		
	Significant Values During the Double-blind Treatment Period		
14.3-6.1	ECG Parameters: Number (%) of Participants with	Safety Population	
14.3-0.1	Post-baseline Potentially Clinically Significant	Safety Population	
	Values		
14.3-7.2.A	C-SSRS: Number (%) of Patients with Suicidal	Safety Population	
17.J-1.2.A	Ideation or Suicidal Behavior During the Double-	Salety i opulation	
	blind Treatment Period		
* Table IDs are based on the Study SAP TFL shell document.			
Table 125 are based on the Study 571 112 shell document.			

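### High BP and pulse values count as outliers only above one fixed cutoff for ages 7-17, so the change criterion seldom decides; add change-only rows by arm and age group

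*SAP*

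**What the plan says.** Table 11-2 in SAP 11.3 gives each of SBP, DBP and pulse an observed-value limit and a change limit, and its footnote joins them: "A postbaseline value is considered potentially clinically significant if it meets both the observed-value and the change-from-baseline criteria". Protocol 9.7.6.3 has the same rule and leaves the cutoffs to the SAP: "Vital sign values will be PCS if they meet both the observed-value criteria and the change from baseline-value criteria".

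- SBP high: at least 140 mm Hg and "Increase of ≥ 20".
- DBP high: at least 100 mm Hg and "Increase of ≥ 15".
- Pulse high: at least 130 bpm and a rise of at least 15.
- Weight, in the same table: a 7% change alone, with no observed-value limit.

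The BP and pulse limits do not vary by age or sex. The supportive listing and the accompanying AE listing in SAP 11.3 cover only patients who have a PCS value. SAP 11.3 also plans descriptive changes from baseline in BP and pulse, by visit and treatment group.

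Elsewhere the SAP counts change alone or adjusts for age. SAP 11.4 counts QTc increases above 30 and above 60 msec alongside the 500 msec limit. SAP 11.5.2 says: "Weight and height will be presented as standardized z-scores adjusted for gender and age". The age groups 7-11 and 12-17 are defined in SAP 8.0 but used only for demographics.

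For the interim analysis, SAP 13.0 lists "PCS for laboratory parameters, vital signs, and ECGs", and the only vital-sign entry in Table 20-2 (Appendix III) is table 14.3-5.1, the PCS count.

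**The concern.** When two conditions are joined by AND, the harder one decides. For a patient whose baseline is well below the cutoff, that is the cutoff, and the stated rises of 20, 15 and 15 have no effect. A child who goes from 100 to 135 mm Hg systolic has risen by 35, well over the SAP's own change limit, yet is in neither the outlier count nor the two listings built on it.

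What is at stake is the usefulness of one safety table. An outlier table should show individuals whose values move a long way, which a mean cannot do. In a paediatric trial with one dosing scheme for ages 7-17, a reader will want to know whether such individuals are more frequent on active drug and whether they cluster in one age group. As planned, the table can answer neither question for most qualifying rises.

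**Working it through.** The documents give no figure to reproduce here, so the check has two parts. Part 1 needs only Table 11-2. Part 2 needs assumptions.

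**1. Rise needed to be counted**

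Rise needed = max(change criterion, cutoff − baseline). The change criterion decides only if baseline ≥ cutoff − change criterion:

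- SBP: 140 − 20 = 120 mm Hg
- DBP: 100 − 15 = 85 mm Hg
- Pulse: 130 − 15 = 115 bpm

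From an illustrative baseline of 100/62 mm Hg and 80 bpm, the rises needed are 140 − 100 = 40, 100 − 62 = 38 and 130 − 80 = 50, against stated criteria of 20, 15 and 15.

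**2. Share of patients affected**

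Assumptions, none from the documents: normal baselines with SD 10 (SBP), 8 (DBP) and 11 (pulse); changes with the same SDs, independent of baseline; correlation 0.5 between a patient's changes; drug shift +5, +4 and +8. The six postbaseline visits are from the schedule of evaluations. A patient counts if any visit qualifies. Simulation of 400,000 patients per scenario gives:

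| Measure | Mean baseline | Change criterion met, with shift | Also reach cutoff, with shift | Change criterion met, no shift | Also reach cutoff, no shift |
|---|---|---|---|---|---|
| SBP | 105 (100-112) | 23.5% | 4.2% (2.0-9.1%) | 9.5% | 1.4% |
| DBP | 65 (60-70) | 28.3% | 1.1% (0.3-3.1%) | 12.1% | 0.3% |
| Pulse | 82 (75-90) | 61.9% | 1.8% (0.5-6.1%) | 28.8% | 0.4% |

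Point values are at the central baseline; the ranges in brackets run over the baselines shown. With the shift, the share of change-criterion patients whom the dual rule leaves out is 1 − (both ÷ change): 61-91% for SBP, 89-99% for DBP and 90-99% for pulse.

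Per 160-patient arm at the central values, drug against placebo, that is for DBP about 45 against 20 patients on change alone (0.283 × 160; 0.121 × 160), and about 2 against 1 or 0 under the dual rule. For pulse it is about 99 against 46, compared with about 3 against 1 or 0.

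**3. Sensitivity**

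A wider grid looked at single rises: change SD 7-12, shift 0 to 10 mm Hg or 0 to 15 bpm, and correlation 0 or −0.4 between baseline and change. The share of qualifying rises that also reach the cutoff is at most 38% for SBP at mean baselines of 95-110, 21% for DBP at 55-70 and 22% for pulse at 75-95. At a mean SBP of 115 it runs from 7% to 55%, so the statement that most rises are missed can fail there.

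**4. What the mean-change tables would show**

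Difference in standard errors = shift ÷ (SD × √(2/160)). SBP: 5 ÷ (10 × 0.1118) = 4.5. DBP: 4 ÷ (8 × 0.1118) = 4.5. Pulse: 8 ÷ (11 × 0.1118) = 6.5.

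**The case against.** The dual criterion is prespecified in the protocol and the SAP follows it. A PCS table is meant for extreme values, while the mean-change tables carry a general shift. That is a fair account of the design, and four points in it limit what can be claimed.

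- A reader might infer that a pressor or heart-rate effect would go unseen at the final analysis, or that the near-empty table would pass as reassurance. The documents do not support this. SAP 11.3 plans changes by visit and arm, and the shifts assumed above would stand 4.5 to 6.5 standard errors from placebo. Findings the Investigator judges clinically significant are AEs (Protocol 9.5.2.1), and SAP 16.4 puts all assessments in the data listings.
- A reader might infer that the youngest children are shown to start lowest on all three measures. No section gives baseline BP or pulse by age. Protocol 9.4.4 does say, after describing ages 7-11, that "80 mg/day is expected to show exposure similar to exposures seen for the adult population administered 120 mg/day". It also expects concentrations to stay within the approved adult range, and the increase to 80 mg/day is optional. This is a reason to look by age group, not evidence of an effect there.
- A reader might infer that unblinded safety review sees vital signs only as PCS counts. That holds for the interim list in SAP 13.0 and Appendix III. Protocol 9.7.8 reports that interim as already conducted, at 62%. The Data Monitoring Committee in Protocol 9.10 works under a charter that is not among these documents.
- Change-only counts include much chance variation: on the assumptions above, 10-29% of patients with no drug shift. This stands, and means that the rows are useful only as a comparison with placebo.

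None of this restores the individual rises to the outlier table. A mean does not count individuals, the planned summaries are not split by age, AE reporting is discretionary, and full listings hold the values without counting them.

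**Conclusion.** The point holds as a gap in reporting. That the change limits decide only from baselines of 120 mm Hg SBP, 85 mm Hg DBP or 115 bpm upward is arithmetic from Table 11-2. That most individual rises are left out of the table and its two listings rests on assumed baselines, SDs and shifts. On those, roughly 60-99% of patients who meet the SAP's own change criterion are not counted. The conclusion weakens if mean SBP is near 115. It does not extend to a hidden overall effect at the final analysis, nor to a demonstrated problem in the youngest children. It is a cheap improvement to the safety reporting and does not threaten the trial's conclusions.

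**What to change.** In SAP 11.3 and table 14.3-5.1, keep the dual-criterion rows. Add rows for patients who meet the existing change criterion alone (SBP rise ≥ 20, DBP rise ≥ 15, pulse rise ≥ 15), by treatment arm, overall and for ages 7-11 and 12-17. This follows the SAP's own handling of QTc increases, uses its own thresholds and age groups, and sets no new clinical limit. State in the table note that the rows include chance variation and are to be read against placebo.

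If any further unblinded safety review takes place, include the by-visit mean changes in BP and pulse. The interim already conducted cannot be altered.

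The cost is a few rows in one table, and one extra table for any further review, all from data already collected. The drawback is the background rate: the rows will show sizeable counts in every arm, and the age split makes each comparison smaller.
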